Dual energy x-ray absorptiometry (DXA) was performed pre- and post-training (36 sessions) in nine of ten participants (one was lost to follow up due to an abrupt change in his school schedule). On average, the group lost total body mass (**Figure 4**). In five participants most of this weight loss was attributed to fat and lean mass loss, but in four participants, the total mass loss was predominantly from fat tissue mass (**Figure 4**). The nine participants demonstrated significant loss of regional and total body fat tissue mass [mean \pm SD (95% confidence limits)]: arms: -236 ± 159 g (-114 to -358 g), $P=0.0021$; legs: -641 ± 493 g, (-262 to -1020 g), $P=0.0045$; trunk: -1030 ± 566 g, (-595 to -1466 g), $P=0.0006$; and total body: -1914 ± 1150 g, (-595 to -2798), $P=0.0011$. Note, the body fat mass losses are strongly supported because the confidence limits were outside of 0 and the power for the total and regional body fat losses was at 100%. Regional and total body lean tissue mass improved in four of nine participants, albeit not statistically significant when analyzed for the total group.

Figure 4. Regional and Total Body Fat and Lean mass and Total Mass changes Pre and Post 36 sessions of Exoskeletal-Assisted walking (N=9).

TB=total body; All nine participants lost fat mass. Four gained lean and five lost lean along with fat mass, which is consistent with the total weight loss. Three of the four who gained lean had zones of partial preservation.

To date, with over 1000 hours of exoskeletal-assisted walking, no study-related serious adverse events (SAEs) occurred during this Phase II clinical trial. In the initial weeks of the clinical trial a few minor skin abrasions were noted that fully resolved with improved fitting and padding²⁴.

Relevance of the study and explain the applicability of the proposed findings:

Mobility: While the USA is one of the best countries in the world for accessibility for the disabled, wheelchair-dependent persons with SCI are at many distinct disadvantages, one of which is the daily loss of the ability to be at eye level with others who are standing. Not all buildings have accessible ramps, and stairs continue present an obstacle for entrance.

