 - ii. 10% in \leq 40 seconds (\geq 0.25 m/s)
 - b. 6min WT
 - i. 80% at a distance of \geq 50 m (\geq 0.14 m/s)
 - ii. 20% at a distance \geq 80 m (\geq 0.22 m/s);
 - c. TUG
 - i. 80% in \leq 120 seconds
 - ii. 20% in \leq 90 seconds

2. By session 36 (three months of WALK training), participants will have improved their ability to walk faster and longer distances and will be able to perform exoskeletal-assisted walking tests with or without minimal assistance as follows:
 - a. 10m WT - 70% in ≤ 40 seconds (≥ 0.25 m/s)
 - b. 6min WT - 70% at a distance ≥ 80 m (≥ 0.22 m/s)
 - c. TUG - 60% in ≤ 90 seconds.

Secondary Aims are to affect the following by three months of exoskeletal-assisted walking (WALK):

1. To improve bowel function as measured by established survey instruments; and
2. To reduce total body fat mass and percent as measured by DXA.

Exploratory Aims:

1. To improve autonomic/cardiovascular function (vagal tone) measured by high frequency component of the 24-hour holter monitor;
2. In persons with T6 and above, to improve orthostatic hypotension (OH) tolerance measured by a standard OH challenge test from supine to seated;
3. To improve HDL-c, Homeostatic Model of Assessment – Insulin Resistance (HOMA-IR), serum total testosterone and estradiol levels measured by serum and plasma assay kits; and
4. To improve quality of life (QOL) measured by item banks from the SCI-QOL and Patient Reported Outcomes Measurement Information System (PROMIS).

Hypotheses

Primary Hypothesis (are tested pre and post the WALK arm only):

1. By session 36, 70% of the participants compared with 10% at session 12 will be able to perform the 10m WT ≤ 40 seconds (≥ 0.25 m/s);
2. By session 36, 70% of the participants compared with 10% at session 12 will be able to perform the 6min WT distance ≥ 80 m (≥ 0.22 m/s); and
3. By session 36, 60% of the participants compared with 20% at session 12 will be able to perform the TUG in ≤ 90 seconds.

Secondary Hypotheses (are tested between the WALK arm and the UA arm, within-subject)

4. Bowel function will improve by 25% using the Ten-Question bowel survey. (Note, the components of this survey represent a 50% reduction in bowel evacuation (BE) time, a 25% increase in BE weekly frequency per week, a 50% reduction in BE medication use, and/or a 25% improvement in stool consistency from harder to softer.)

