Methods for recruiting subjects: Three sites will participate in this study: 1) JJPVAMC will be the Lead Site and has four ReWalk units; 2) UMROI will be a sub award site and has two ReWalk units with the potential to acquire two additional units through collateral funding and 3) KFRC will be a sub site of the JJPVAMC through the satellite Center of the Spinal Cord Damage Research Center which is located at Kessler Institute of Rehabilitation. KFRC has one Ekso unit. The JJPVAMC and KFRC study sites each have close to 3 years of experience conducting studies using the exoskeletal systems for persons with SCI. UMROI has recently acquired two ReWalk units and has experience conducting a DOD CDMRP Clinical Trial in persons with SCI. UMROI has begun to study the ReWalk in their patients. Potential participants will be recruited from the research databases at each institution and from the clinical outpatient services. At the UMROI site, the principal investigator also is the Director of the SCI support team clinic at the Baltimore VA Medical Center, so he will be able to recruit from both a civilian and a veteran population. Currently, both the JJPVAMC and KFRC have a waiting list of participants who have contacted either Center to become involved an exoskeletal-assisted walking program. All three study sites have a positive and significant history of recruiting and conducting ethically appropriate clinical trials in persons with SCI.

Expected withdrawal rates: In 13 participants enrolled to date at the JJPVAMC, three withdrew (one due to job relocation, one due to an unrelated medical illness, and one due to difficulty with travel). It is expected that these and/or similar reasons will affect the compliance and attendance of this study to some degree. As such a total of 132 participants will be enrolled as follows: JJPVAMC (n=28, T3 and below), KFRC (n=16, T2 and above) and UMROI (n=20, T3 and below). An enrollment schedule by site is provided (**Table 4**).

Table 4. Original Enrollment Schedule by Site

Study Sites and Groups		Y1				Y2				Y3				Y4				Sub Total
		Q1	Q2	Q3	Q4													
JJPVAMC (T3 and below, ReWalk)	Group 1			2			4			4			4					14
	Group 2			2			4			4			4					14
	subtotals			4			8			8			8					28
JJPVAMC at KFRC (C5 to T2, Ekso)	Group 1			2			2			2			2					8
	Group 2			2			2			2			2					8
	subtotals			4			4			4			4					16
UMROI (T3 and below, ReWalk)	Group 1			2			3			3			2					10
	Group 2			2			3			3			2					10

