	subtotals			4			6			6			4					20
Total Participants by Year				12		18				18				16				64

Group assignment process: Participants will be block randomized within site.

Statistical Plan and Data Analysis:

The best value achieved for each walking test during sessions 5 to 12 (T1) and from 13 to 36 (T2) will be recorded separately to be used for comparative analysis. These best T1 and T2 scores will be used to determine

percent of occurrence with the hypothesized goals. Achievement of the hypothesized goals in the WALK intervention group for the primary outcomes (10mWT, 6minWT and TUG at the 12- and 36-session time points) will be reported as categorical data and presented as a percent of occurrence with the 95% upper and lower confidence intervals (CI). Continuous variables for the Secondary outcomes of the body composition and bowel function variables will be presented as mean \pm SD. For the continuous variables, a difference score or percent change from pre to post will be calculated for the WALK and UA arms of the study. Comparisons between WALK (Pre-Post) vs. UA (Pre-Post) difference scores will be performed using paired t-tests. Pre to post comparisons for variables that are not normally distributed will be performed by non-parametric tests such as the Wilcoxon signed rank test or the paired sign test.

Walking outcomes (10mWT, 6minWT, and TUG): Achievement of the hypothesized goals in the WALK intervention group will be reported as categorical data and presented as percent occurrence with 95% confidence intervals (CI). For each of these outcomes, the best value achieved during the T1 period (sessions 5-12) and the T2 period (sessions 13-36) will be recorded separately and compared to the hypothesized goals, as listed below:

Primary Hypothesis (are tested pre and post the WALK arm only):

1. By session 36, 70% of the participants compared with 10% at session 12 will be able to perform the 10m WT \leq 40 seconds (\geq 0.25 m/s);
2. By session 36, 70% of the participants compared with 10% at session 12 will be able to perform the 6min WT distance \geq 80 m (\geq 0.22 m/s); and
3. By session 36, 60% of the participants compared with 20% at session 12 will be able to perform the TUG in \leq 90 seconds.

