Power Calculation: A one-sample method was chosen to test the observed proportion against the expected proportion determined from the preliminary data of the percent of those who achieved these goals. Using the most stringent criteria above of 20% (session 12) versus 60% (session 36) who achieve the TUG goal, there is 100% power (alpha=5%, double sided Z-power=5.6) with 13 of 63 (20%) versus 38 of 64 (60%) achieving the goal. If the attrition rate is as high as 25%, then the power is still 100%, (alpha=5%, double sided Z-power=4.53), with 10 of 48 (20%) at session 12 versus 29 of 48 (60%) of the participants achieving the goal at session 36.

Secondary Hypotheses

1. Bowel function will improve as demonstrated by 25% improvement on the Ten-question bowel survey.
2. Total body fat mass is hypothesized to be reduced by 2.0 ± 1.2 kg

Power Calculation: The preliminary data demonstrated a total score change of 31.5 ± 7.1 to 22.5 ± 5.3 , N=8 and a total body fat mass change from 24.14 ± 8.45 to 22.22 ± 8.19 , N=9, alpha=0.05, using a pairwise method, the power for both was 100%. Allowing for 25% dropout, the power is still 100% for 48 participants at an alpha=0.05.

Please note, that both the primary and secondary hypotheses are well powered due to the huge effect observed in the preliminary data. However, performing this study in fewer participants will not permit us to ask many of the exploratory questions. There is no empirical data to support an appropriate power calculation for the exploratory hypotheses.

References

2. Spungen, A. M., Adkins, R. H., Bauman, W. A., Kemp, B. J. & Waters, R. L. The effects of level and completeness of lesion on body composition in subjects with spinal cord injury. *J Spinal Cord Med* **22**, 43 (1999).

3. Spungen, A. M., Wang, J., Pierson, R. N. & Bauman, W. A. Soft tissue body composition differences in monozygotic twins discordant for spinal cord injury. *J. Appl. Physiol.* **88**, 1310–5 (2000).
4. Wahman, K. *et al.* Cardiovascular disease risk factors in persons with paraplegia: the Stockholm spinal cord injury study. *J Rehabil Med* **42**, 272–278 (2010).

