# A Randomized, Crossover Clinical Trial of Exoskeletal-assisted Walking to Improve Mobility, Bowel Function and Cardio-Metabolic Profiles in Persons with SCI

## Statistical Plan and Data Analysis:

The best value achieved for each walking test during sessions 5 to 12 (T1) and from 13 to 36 (T2) will be recorded separately to be used for comparative analysis. These best T1 and T2 scores will be used to determine percent of occurrence with the hypothesized goals. Achievement of the hypothesized goals in the WALK intervention group for the primary outcomes (10mWT, 6minWT and TUG at the 12- and 36-session time points) will be reported as categorical data and presented as a percent of occurrence with the 95% upper and lower confidence intervals (CI). Continuous variables for the Secondary outcomes of the body composition and bowel function variables will be presented as mean  $\pm$ SD. For the continuous variables, a difference score or percent change from pre to post will be calculated for the WALK and UA arms of the study. Comparisons between WALK (Pre-Post) vs. UA (Pre-Post) difference scores will be performed using paired t-tests. Pre to post comparisons for variables that are not normally distributed will be performed by non-parametric tests such as the Wilcoxon signed rank test or the paired sign test.

**Walking outcomes (10mWT, 6minWT, and TUG):** Achievement of the hypothesized goals in the WALK intervention group will be reported as categorical data and presented as percent occurrence with 95% confidence intervals (CI). For each of these outcomes, the best value achieved during the T1 period (sessions 5-12) and the T2 period (sessions 13-36) will be recorded separately and compared to the hypothesized goals, as listed below:

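### The secondary WALK-versus-UA test omits sequence and site although participants are randomised to sequence within site; the interval is wider than needed if the difference varies by either

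*Protocol*

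**What the plan says.** Under Group assignment process the protocol says "Participants will be block randomized within site". The Research design paragraph gives the two sequences: 32 participants have WALK then UA, and 32 have UA then WALK.

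The analysis text is the same in the protocol and the SAP (Statistical Plan and Data Analysis): "Comparisons between WALK (Pre-Post) vs. UA (Pre-Post) difference scores will be performed using paired t-tests". Wilcoxon signed rank or paired sign tests are named for variables that are not normally distributed. Neither document puts site, sequence or period into any analysis.

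The scope is set in the protocol's Hypotheses section. The between-arm comparison belongs to the secondary outcomes: "Secondary Hypotheses (are tested between the WALK arm and the UA arm, within-subject". The walking outcomes do not use it: "Primary Hypothesis (are tested pre and post the WALK arm only".

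Two further statements matter:
- Exploratory Hypotheses 1 and 2 expect Group 1's bowel improvement to be gone by one month of UA, and its fat change to be gone by three months.
- The Expected withdrawal rates paragraph and Table 4 tie site to lesion level and device. They give "KFRC (n=16, T2 and above" on the Ekso; the other two sites (28 and 20) take T3 and below on the ReWalk.

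**The concern.** Sequence and site structure the allocation, so one expects them in the analysis. When they are left out, any variation in the WALK-minus-UA difference between sequences or between sites goes into the error term of the paired t-test.

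The documents give reason to expect such variation. If Group 1 regains fat during UA, its UA change differs from Group 2's. The Ekso's stated maximum velocity is 0.45 m/s against 0.80 m/s for the ReWalk. The pilot reports 0.17 m/s in four Ekso users, against 0.27 to 0.33 m/s on the ReWalk by session 36. The protocol also says that the medical outcomes probably depend on being able to walk in the device.

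At stake are the width of the secondary-outcome intervals and whether a difference in effect between sites or sequences would be seen at all.

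**Working it through.** **Inputs from the documents**
- Fat mass: "Total body fat mass is hypothesized to be reduced by 2.0 ± 1.2 kg"; pilot change "total body: -1914 ± 1150 g" (N=9). Both SDs are for a single pre-post change, not for WALK minus UA.
- Bowel score: "31.5 ± 7.1 to 22.5 ± 5.3" (N=8), a change of 9.0 points.
- Sites 28, 16 and 20; sequences 32 and 32. Both add to 64, which is used here although the text also says 132. KFRC's share is 16/64 = 0.25.

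**Assumptions (not in the documents)**
- SD of the WALK-minus-UA difference D, within sequence and site: s = 1.2 kg, or 1.2 × √2 ≈ 1.7 kg.
- h, half the difference in mean D between the two sequences: 0 to 1.0 kg.
- g, the difference in mean D between KFRC and the other two sites: 0 to 1.0 kg.

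**The plan's own figure.** The stated power is 100% with 48 participants (paired, alpha 0.05, taken as two-sided).
- Fat mass: noncentrality 1.92/1.15 × √48 = 11.6 against a critical value of 2.01.
- Bowel: with a pre-post correlation of 0 the SD of change is √(7.1² + 5.3²) = 8.86, and noncentrality is 9.0/8.86 × √48 = 7.0. A higher correlation raises it.
- Power exceeds 99.99% in each case, so the figure is reproduced.

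**What pairing removes.** A site effect common to both arms appears in both terms of D and cancels. In a simulation of 4,000 trials, a 3 kg site shift in both periods left the half-width at 0.298 kg with and without the site term.

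**What pairing leaves**
- Paired t-test: variance of D = s² + h² + 0.25 × 0.75 × g², with n − 1 = 63 df.
- Regression on sequence and site: variance s², with n − 4 = 60 df.

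Approximate 95% half-widths at n = 64 are t × SD/√64, with t = 1.998 (63 df) and 2.000 (60 df):

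| s (kg) | h | g | SD in paired test | Paired | Adjusted | Excess |
|---|---|---|---|---|---|---|
| 1.2 | 0 | 0 | 1.200 | 0.300 | 0.300 | 0% |
| 1.2 | 0 | 1.0 | √1.6275 = 1.276 | 0.319 | 0.300 | 6% |
| 1.2 | 0.5 | 0 | √1.69 = 1.300 | 0.325 | 0.300 | 8% |
| 1.2 | 1.0 | 0 | √2.44 = 1.562 | 0.390 | 0.300 | 30% |
| 1.7 | 0 | 1.0 | √3.0775 = 1.754 | 0.438 | 0.425 | 3% |
| 1.7 | 1.0 | 0 | √3.89 = 1.972 | 0.493 | 0.425 | 16% |

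The ratios are nearly the same at n = 48.

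**Where h = 1.0 kg comes from.** Take a 2.0 kg loss in WALK, full regain in Group 1 during UA, and no UA change in Group 2. Then D = −2 − 2 = −4 kg in Group 1 and −2 − 0 = −2 kg in Group 2, so h = (4 − 2)/2 = 1.0 kg.

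The same reasoning for the bowel score gives h = 4.5. With an assumed SD of D from 4.28 (correlation 0.8, UA adding no variance) to 12.53 (correlation 0, times √2), the excess is √(1 + 4.5²/4.28²) − 1 ≈ 45% down to √(1 + 4.5²/12.53²) − 1 ≈ 6%.

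**What a sequence term does not do.** Under full regain the pooled mean of D is (−4 − 2)/2 = −3 kg against a WALK effect of −2 kg. It is −3 kg with or without the sequence term; only the interval around it narrows.

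**Power.** In the least favourable case with n = 48 (s = 1.7, h = g = 1.0), the SD is √4.0775 = 2.02 and noncentrality 2.0/2.02 × √48 = 6.9. Power for 2.0 kg still exceeds 99.99%.

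**The case against.** The strongest reply is that the crossover makes each participant his or her own control, so the paired test already deals with site. That stands for site main effects. It does not cover a WALK effect that differs by site, or a period or sequence difference.

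It can also be said that the documents give no fat-mass effect by site or device and no period shift, so every size above is an assumption. That stands too. A reader might infer a large loss from site by supposing that Ekso users lose no fat against 1.92 kg on the ReWalk. The added variance is then 0.1875 × 1.92² = 0.69, or 26% to 52% of the within-site variance for an SD of 1.63 to 1.15 kg. Nothing in the documents supports a zero Ekso effect, and the 52% end treats the UA period as adding no variability.

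Nor is the paired t-test the only comparison: rank and sign tests are named, the exploratory hypotheses address Group 1 separately, and Group 2's lead-in is meant to show stability. None of these puts sequence or site into the between-arm estimate.

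Finally, the regain that the protocol predicts is a question of bias more than of precision. That is right, and it is why a sequence term alone is not enough.

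**Conclusion.** The omission is real, and its effect on precision is conditional. For fat mass, with an assumed SD of the difference of 1.2 to 1.7 kg and 64 participants, the paired interval is 0% wider with neither effect, about 3% to 6% wider for a 1 kg site difference in effect, and about 16% to 30% wider for a 1 kg half-difference between sequences. The sequence part is the better founded, because the protocol itself predicts the reversal that would cause it.

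Three stronger readings are not supported:
- That the standard errors are too large as a matter of fact. They are so only if D varies by sequence or site.
- That the primary outcomes or the stated power are affected. The primary outcomes do not use this test, and secondary power stays at about 100%.
- That a site term would isolate the device effect. At KFRC site, device and lesion level coincide.

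This is a modest, cheap improvement to the secondary analyses.

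**What to change.** In the Statistical Plan and Data Analysis section of both documents, replace the paired t-test by a linear regression of each participant's WALK-minus-UA difference on sequence and site. Code sequence −1/+1 and centre the site indicators by site size, so that the intercept is the overall effect. With ordinary reference coding the intercept would be one site's effect.

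A mixed model with arm, period, sequence, site and a site-by-arm term is equivalent if the overall effect is weighted in the same way. Without the site-by-arm term it recovers none of the precision lost to site, because a site main effect does not enter the within-participant contrast.

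Show the estimate by site, labelled descriptive. Report the between-group comparison of first-period changes as a sensitivity analysis, since regain or carry-over cannot affect it.

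Cost: 63 − 60 = 3 degrees of freedom, SAP wording and one extra model. With neither effect present the half-width stays at 0.300 kg. The first-period comparison is less precise: at an SD of change of 1.2 kg its half-width is about 2.0 × 1.2 × √(2/32) = 0.60 kg, which is adequate for a sensitivity check on a 2.0 kg effect.

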# A Randomized, Crossover Clinical Trial of Exoskeletal-assisted Walking to Improve Mobility, Bowel Function and Cardio-Metabolic Profiles in Persons with SCI

## Statistical Plan and Data Analysis:

The best value achieved for each walking test during sessions 5 to 12 (T1) and from 13 to 36 (T2) will be recorded separately to be used for comparative analysis. These best T1 and T2 scores will be used to determine percent of occurrence with the hypothesized goals. Achievement of the hypothesized goals in the WALK intervention group for the primary outcomes (10mWT, 6minWT and TUG at the 12- and 36-session time points) will be reported as categorical data and presented as a percent of occurrence with the 95% upper and lower confidence intervals (CI). Continuous variables for the Secondary outcomes of the body composition and bowel function variables will be presented as mean  $\pm$ SD. For the continuous variables, a difference score or percent change from pre to post will be calculated for the WALK and UA arms of the study. Comparisons between WALK (Pre-Post) vs. UA (Pre-Post) difference scores will be performed using paired t-tests. Pre to post comparisons for variables that are not normally distributed will be performed by non-parametric tests such as the Wilcoxon signed rank test or the paired sign test.

**Walking outcomes (10mWT, 6minWT, and TUG):** Achievement of the hypothesized goals in the WALK intervention group will be reported as categorical data and presented as percent occurrence with 95% confidence intervals (CI). For each of these outcomes, the best value achieved during the T1 period (sessions 5-12) and the T2 period (sessions 13-36) will be recorded separately and compared to the hypothesized goals, as listed below:

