5. Total body fat mass is hypothesized to be reduced on average by 9 ± 7 percent (an average of 1.9 ± 1.2 kg decrease from baseline).

Exploratory Hypotheses:

1. In Group 1 (WALK first), the bowel improvement changes will return to baseline values by one month of the UA arm.
2. In Group 1 (WALK first), the body fat mass and percent changes will return to baseline values by 3 months of the UA arm.
3. Associated with increased activity, there will be improved autonomic/cardiovascular function (vagal tone) as measured by the high frequency component of the holter monitor recordings and the tolerance to orthostatic challenge.
4. Associated with increased activity and fat mass loss, there will be statistically significant improvement in HDL-c, HOMA-IR, serum total testosterone and estradiol levels
5. Quality of life (using select SCI-QOL item banks) will be reported to be improve after in the WALK arm, but not for the UA arm

Safety concerns with the use of the exoskeletal devices will continue to be evaluated. Any serious (SAEs) or adverse events (AEs) will be recorded and reported the appropriate oversight bodies.

Study Design

Research design: A Phase III randomized clinical trial (RCT) will be performed using a crossover design and employing an exoskeletal-assisted walking intervention. The experimental arm will be compared to a usual activities (UA) arm, as the control, in 132 persons with chronic SCI (>6 month post injury) who are wheelchair-dependent for outdoor mobility in the community. Eligible participants will be randomized (within site) to one of two groups for 12 weeks (three months): Group 1 (n=32) will receive exoskeletal-assisted walking (WALK) first for 12 weeks then crossover UA for a second 12 weeks; Group 2 (n=32) will receive UA first for 12 weeks then cross-over to the WALK arm for 12 weeks of training. The WALK arm will consist of supervised exoskeletal-assisted walking training, three sessions per week (4-6 h/week) for 36 sessions for their second 12-week period. The UA arm will consist of identification of usual activities for each participant, encouragement to continue with these activities and attention by study team members throughout the 12-week UA arm. These activities will be recorded in a weekly log. A fixed answer format will be used to capture this information.

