## Secondary Hypotheses

1. Bowel function will improve as demonstrated by 25% improvement on the Ten-question bowel survey.
2. Total body fat mass is hypothesized to be reduced by  $2.0 \pm 1.2$  kg

**Power Calculation:** The preliminary data demonstrated a total score change of  $31.5 \pm 7.1$  to  $22.5 \pm 5.3$ , N=8 and a total body fat mass change from  $24.14 \pm 8.45$  to  $22.22 \pm 8.19$ , N=9, alpha=0.05, using a pairwise method, the power for both was 100%. Allowing for 25% dropout, the power is still 100% for 48 participants at an alpha=0.05.

Please note, that both the primary and secondary hypotheses are well powered due to the huge effect observed in the preliminary data. However, performing this study in fewer participants will not permit us to ask many of the exploratory questions. There is no empirical data to support an appropriate power calculation for the exploratory hypotheses.

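### The secondary WALK–UA contrast measures change from each arm's own start, so benefit lost during UA in Group 1 is counted as extra WALK effect; the optional percent scale adds a little more

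*SAP*

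**What the plan says.** The SAP section Statistical Plan and Data Analysis, repeated in the protocol section of the same name, states for continuous secondary outcomes that "a difference score or percent change from pre to post will be calculated for the WALK and UA arms of the study". It continues: "Comparisons between WALK (Pre-Post) vs. UA (Pre-Post) difference scores will be performed using paired t-tests". No rule assigns one scale to each outcome.

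The hypotheses use both scales. For bowel, the SAP (Secondary Hypotheses) has "Bowel function will improve as demonstrated by 25% improvement on the Ten-question bowel survey", a percent. For fat mass, the protocol's statistical section has "Total body fat mass is hypothesized to be reduced by 2.0 ± 1.2 kg", while its Hypotheses section gives 9 ± 7 percent together with 1.9 ± 1.2 kg.

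Three design facts matter:
- Group 1 goes from WALK to UA with no washout described.
- DXA is done at entry, at crossover and after the second arm. The bowel survey is given before each arm and bi-weekly. The pre-UA value in Group 1 is therefore a post-WALK value (protocol, Study Design and Description of Assessments).
- The protocol's Exploratory Hypotheses expect Group 1 to be back at baseline by one month of UA for bowel and by three months of UA for fat mass. Preliminary Studies reports that the pilot bowel gain had gone one month after walking stopped.

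**The concern.** A change score within each arm is a fair measure of that arm only if the arm starts from a comparable state. Here Group 1 starts UA already improved. If it then drifts back, the UA change is a worsening of the same size as the WALK gain. Subtracting it counts one effect twice in half of the sample.

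The percent option makes this slightly worse, because the return is divided by a smaller starting value than the fall was. What is at stake is the size of the bowel and fat-mass effects that readers take from the trial. Whether the tests reach significance is not the issue.

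**Working it through.** **The plan's own figure.** The SAP claims 100% power for both secondary outcomes with 48 participants, by a paired method. This reproduces (two-sided alpha 0.05 assumed). Fat mass, with standardized effects from 1.9/1.2 = 1.58 to 2.0/1.2 = 1.67, gives 100%. Bowel gives 99.99–100% when the unstated pre-post correlation is varied from -0.5 to 0.9.

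**Inputs.** Pilot bowel score 31.5 to 22.5, a fall of 9 points. Pilot fat mass 24.14 to 22.22 kg, a fall of 1.92 kg (both from the power calculation for the secondary hypotheses). Assumptions: equal groups, no change during UA in Group 2, and full reversal during UA in Group 1.

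**Bowel, difference score.**
- Group 1: WALK -9, UA +9, contrast -18.
- Group 2: UA 0, WALK -9, contrast -9.
- Pooled: (-18 - 9)/2 = -13.5. Against -9 the ratio is 1.50.

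**Bowel, percent change.**
- The fall is -9/31.5 = -28.6%; the return is +9/22.5 = +40.0%.
- Group 1: -28.6 - 40.0 = -68.6%. Group 2: -28.6%.
- Pooled: -48.6%. Against -28.6% the ratio is 1.70.
- Part due to scale alone: -13.5/31.5 = -42.9%, and 48.6/42.9 = 1.13.

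Simulations with individual variation put the pooled percent contrast between about -50% and -56%. They depend on assumed SDs and correlations, so the figure from the means is the one to rely on.

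**Fat mass.**
- Difference score: (-3.84 - 1.92)/2 = -2.88 kg against -1.92 kg, ratio 1.50.
- Percent change: -1.92/24.14 = -7.95% and +1.92/22.22 = +8.64%. Group 1 is -16.59%, Group 2 is -7.95%, pooled -12.27%.
- Part due to scale alone: -2.88/24.14 = -11.93%, and 12.27/11.93 = 1.03.

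**End-of-arm value instead.** Let f be the share of the Group 1 gain lost during UA. The pooled bowel contrast is -9 - 4.5f for change from each arm's start, and -4.5 - 4.5f for the end-of-arm value.

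| f | Change from arm's start | End-of-arm value |
|---|---|---|
| 1 (full reversal) | -13.5 | -9.0 |
| 0.5 | -11.25 | -6.75 |
| 0 (full persistence) | -9.0 | -4.5 |

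Group 2 alone gives -9 in every row, on either variable.

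**Precision.** Take three visits with SD 7.1 and an assumed common correlation of 0.5.
- End-of-arm contrast: variance 2 × 7.1² × 0.5, SD 7.1.
- Change-score contrast (twice the crossover value minus the entry and final values, up to sign): variance 6 × 7.1² × 0.5 = 151.2. Under full reversal the two group means differ by 9, which adds 4.5² = 20.25. The SD is √171.5 = 13.1.

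**Noise on the percent scale.** From the protocol's Hypotheses section, fat mass has a standardized effect of 9/7 = 1.29 in percent and 1.9/1.2 = 1.58 in kg. Percent is about 19% smaller.

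**The case against.** **The tested scale is already named.** The sentence after the open choice assigns the paired t-test to difference scores. This largely stands, and it makes a free choice of scale after the data are seen a small matter. It leaves two gaps: the bowel hypothesis, worded only in percent, then has no test on its own scale; and naming the difference score does nothing about the arm-specific baseline, which causes most of the overstatement.

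**Reversal is only an exploratory hypothesis.** True, and the overstatement depends on it. But it is the sponsor's stated expectation for both outcomes and, for bowel, it has pilot support. The primary estimate of a secondary effect should not be wrong in the case the protocol predicts.

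**The alternative has its own bias.** This stands too. Under full persistence, change from each arm's start gives exactly -9 and the end-of-arm value gives -4.5. The two biases are equal at half reversal (2.25 points each). The preference for the end-of-arm value rests on the expected reversal and on its smaller SD.

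**Power is ample.** Agreed. Even for the WALK–UA fat contrast, power at 48 is at least 99.9% on either scale, if the UA change has the same SD and the two changes correlate between -0.5 and 0.5.

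**Conclusion.** The point holds as a conditional bias in the estimated effect. If Group 1 returns fully to baseline during UA, the planned contrast is 50% too large on the difference scale for either outcome. On the percent scale it is 70% too large for bowel. The result rests on the pilot means, equal groups and a stable UA arm in Group 2. With partial reversal the excess falls in proportion, to nothing if benefit persists.

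Four stronger readings are tempting, and the documents do not support them:
- *Percent change favours WALK in general.* Its extra noise lowers the standardized effect. With no effect, the upward shift in percent change appears equally in both arms (simulated at about 0.2% for fat mass and 2.1% for bowel) and cancels in the contrast.
- *The open scale seriously inflates false positives.* Reporting the better of the two scales raises type I error from 5% to only about 5.3–6.6% in simulation, and only if the difference-score sentence is set aside.
- *Percent change needs far more participants than a baseline-adjusted analysis.* That compares SDs within a single arm. In a within-person contrast the study-entry value is constant for each person and cancels, so adjusting for it adds little.
- *The whole 70% is due to the percent scale.* The scale accounts for a factor of 1.13; the arm-specific baseline accounts for 1.50.

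**What to change.** In the SAP and in the protocol's matching section:
1. Name one tested variable for the 10Q BFS total and for total body fat mass: the absolute value at the end of each arm, compared within person between WALK and UA. For the bi-weekly bowel survey, say which assessment closes each arm. The study-entry value may be included, but little gain in precision should be claimed for it.
2. Label percent change as descriptive.
3. Put the hypotheses on that scale in the protocol's Hypotheses and statistical sections and in the SAP's Secondary Hypotheses. The 25% bowel target would become a number of points; on the pilot mean it is 0.25 × 31.5 = 7.9. Reconcile 1.9 kg with 2.0 kg for fat mass.
4. Report the Group 1 and Group 2 contrasts separately beside the pooled one. Group 2 is not affected by reversal or persistence, and Group 1 shows how much benefit was lost.

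The cost is wording, with no new visits or data. The price is a smaller stated effect, and attenuation towards half (-4.5 instead of -9 for bowel) if the WALK benefit persists through UA. Item 4 is there to reveal that.
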